8.1.3 Presentation of Statistics

The number of decimal places displayed in effectiveness and safety listings will be determined by the number of decimal places in the raw data.

- All calculated values will be rounded to two decimal places.
- A p-value will be displayed to four decimal places. If a p-value is less than 0.0001, it will be displayed as '<0.0001'.
- Unless otherwise specified, 95% confidence intervals will be calculated using the exact binomial distribution according to Clopper-Pearson's method.

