8.2 STATISTICAL ANALYSES

8.2.1 Demographics and baseline characteristics

8.2.1.1 Demographics and underlying disease information

- Age(years)
- Elderly(≥ 65 years)
- Gender: Male | Female
- Height(cm)
- Weight(kg)
- Body Surface Area(m^2 , Mosteller formula)

$$= \sqrt{\frac{W \times H}{3600}} = 0.016667 \times W^{0.5} \times H^{0.5}$$
- Pregnancy: Yes | No | NA
- Breast-feeding: Yes | No | NA
- Diagnosis:

- Philadelphia (+) B-cell ALL | Philadelphia (-) B-cell ALL | Unknown
- Duration of disease(day):
BESPONSA® administration start date – First diagnosis date + 1
- Current disease status:
Refractory | First relapsed | Second relapsed | Third or more relapsed
- Hepatic disorder: Yes | No
- Renal disorder: Yes | No

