8.2.2.2 Factor analysis for adverse events

To identify factors that may be associated with AEs, AEs according to the background factors in section 8.2.1 and special population set in section 5.3 shall be summarized using the number of subjects(n), percentage(%), number of events and the 95% confidence interval of percentage. In addition, to explore the factors that affect the occurrence of AE, univariate analyses based on a Chi-square test or Fisher's exact test(when cells with an expected frequency of less than 5 exceed 20% of total cells) and logistic regression shall be used to assess the impact of each background factor on the AE occurrence and p-value will be provided.

For the final re-examination report, potentially significant factors(p-value<0.05) identified in the univariate analyses will be further explored in a multiple logistic regression model. For final models, odds ratio, 95% confidence interval of odds ratio and p-value will be provided for each factor. If there is no potential significant factor identified in the univariate analyses, multivariate analysis with logistic regression will not be applied.

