8.2.3.3 Factor analysis of last effectiveness

To identify factors that may be associated with last effectiveness, last effectiveness according to the background factors in section 8.2.1 and special population set in section 5.3 shall be summarized using the number of subjects(n), percentage(%) and 95% confidence interval of percentage. In addition, to explore the factors that affect last effectiveness, univariate analyses based on a Chi-square test or Fisher's exact test (when cells with an expected frequency of less than 5 exceed 20% of total cells) and logistic regression shall be used to assess the impact of each background factor on the last effectiveness and p-value will be provided.

For the final re-examination report, potentially significant factors(p-value<0.05) identified by in the univariate analyses will be further explored and tested in a multiple logistic regression model. For final models, odds ratio, 95% confidence interval of odds ratio and p-value will be provided for each factor. If there is no potential significant factor identified in the univariate analyses, multivariate analysis with logistic regression will not be applied.

PFIZER CONFIDENTIAL

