9. LIST OF TABLES AND TABLE SHELLS

Section I. Analysis for MFDS

Table 1. Patient disposition

Table 2. Demographics and underlying disease information

Table 3. Previous systemic therapy

Table 4. Previous hematopoietic cell transplant

Table 5. Past disease

Table 6. Present disease

Table 7. Veno-occlusive liver disease/Sinusoidal obstruction syndrome(VOD/SOS)

Table 8. Hepatic disorder

Table 9. Renal disorder

Table 10. Allergic history

Table 11. Concomitant medication

Table 12. Administration status of BESPONSA® – Total

Table 13. Summary of Adverse Events

Table 14. Adverse event – AE·ADR

Table 15. Adverse event – Serious AE·ADR

Table 16. Adverse event – Unexpected AE·ADR

Table 17. Adverse event – Unexpected serious AE·ADR

Table 18. Characteristics of adverse events

Table 19. Adverse events by Severity by SOC/PT

Table 20. Adverse events by Action taken by SOC/PT

Table 21. Adverse events by SAE categories by SOC/PT

Table 22. Adverse events by Outcome by SOC/PT

Table 23. Adverse events by Causality to the study drug by SOC/PT

Table 24. Adverse events by Other causality by SOC/PT

Table 25. Categorical factor analysis for adverse events

Table 26. Continuous factor analysis for adverse events

Table 27. Multiple logistic regression for adverse event for the final re-examination

Table 28. Adverse event in elderly(≥65 years) group

Table 29. Adverse event in hepatic disorder group

Table 30. Adverse event in renal disorder group

Table 31. Response evaluations

Table 32. Last effectiveness

Table 33. Categorical factor analysis for last effectiveness

Table 34. Continuous factor analysis for last effectiveness

Table 35. Multiple logistic regression for last effectiveness for the final re-examination

Table 36. Effectiveness(Best overall response)

Table 37. Categorical factor analysis for effectiveness(best overall response)

Table 38. Continuous factor analysis for effectiveness(best overall response)

Table 39. Multiple logistic regression for effectiveness(best overall response) for the final re-examination

Table 40. Non-safety population – AE·ADR

Table 41. Non-safety population – Serious AE·ADR

Table 42. Non-safety population – Unexpected AE·ADR

Table 43. Non-safety population – Unexpected serious AE·ADR

Table 44. Non-PMS Analyses – AE·ADR

Table 45. Non-PMS Analyses – Serious AE·ADR

Table 46. Non-PMS Analyses – Unexpected AE·ADR

Table 47. Non-PMS Analyses – Unexpected serious AE·ADR

Section II. Analysis for publication

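### No increment is stated for the odds ratio of disease duration: on its per-day scale, two-decimal rounding can print a significant effect as about 1.00 (1.00 to 1.00)

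*SAP*

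**What the plan says.** SAP 8.2.1.1 labels duration of disease in days and derives it as "BESPONSA® administration start date – First diagnosis date + 1". It gives no categories, transformation or other unit, although it does list categories for items such as current disease status.

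The factor analyses draw on the whole of 8.2.1. SAP 8.2.2.2 covers "AEs according to the background factors in section 8.2.1 and special population set in section 5.3"; 8.2.3.3 and 8.2.3.6 do the same for last effectiveness and best overall response. Each section runs univariate logistic regression beside the chi-square or Fisher test, and carries factors with p<0.05 into a multiple logistic model for the final re-examination report. The promised output is: "For final models, odds ratio, 95% confidence interval of odds ratio and p-value will be provided for each factor". No section states the increment to which an odds ratio refers.

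SAP section 9 has separate tables for continuous factors, among them "Table 26. Continuous factor analysis for adverse events" and "Table 34. Continuous factor analysis for last effectiveness"; Table 38 is the counterpart for best overall response. The multiple models are in Tables 27, 35 and 39.

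SAP 8.1.3 fixes the display: "All calculated values will be rounded to two decimal places". The only other precision set for a calculated statistic is for p-values: "A p-value will be displayed to four decimal places". A further sentence ties decimals in listings to the raw data, but an odds ratio is a calculated value, so that sentence does not exempt it.

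**The concern.** A logistic coefficient for a variable held in days gives an odds ratio per day, and one day is a tiny step for disease duration. The odds ratio is then so close to 1 that the second decimal cannot show it, even when the effect over a year is large.

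A factor retained because its p-value is below 0.05 could then stand in the final table with an odds ratio and interval that look like no effect, estimated with perfect precision. The p-value survives at four decimals but carries neither size nor direction. SAP section 4 says that p-values will not support definite conclusions, so the estimate and interval have to carry the interpretation, and these are what the rounding removes.

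**Working it through.** The SAP states no odds ratio or effect size for this analysis, so there is no figure to reproduce.

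**Inputs from the documents:** duration in days (SAP 8.2.1.1); two decimals for calculated values (8.1.3); entry to the multiple model at p<0.05 (8.2.2.2, 8.2.3.3, 8.2.3.6); 100 patients (SAP 2.1).

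**Inputs assumed, because the documents do not give them:** SD of duration 100 to 1,460 days; outcome proportion p of 0.5, 0.7 or 0.9; analysis set N of 60 to 100.

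**Step 1. Rounding bound, given a per-day increment.** An odds ratio per day prints as 1.00 if it lies between 0.995 and 1.005. Per year these bounds are:

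- 1.005^365.25 = 6.18
- 0.995^365.25 = 0.16

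A per-year odds ratio of 2 is 2^(1/365.25) = 1.0019 per day, and one of 5 is 1.0044 per day. Both print as 1.00. This step needs no assumption about the data.

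**Step 2. One result on both scales.** Use the approximation SE per SD = 1/√(N·p·(1−p)). With N = 100 and p = 0.5 it is 0.200. Take z = 3, so the coefficient per SD is 0.600, and SD = 730 days.

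- Per day: exp(0.600/730) = 1.00082, limits exp((0.600 ± 1.96 × 0.200)/730) = 1.00028 and 1.00136. Printed: 1.00 (1.00 to 1.00).
- Per year, with the exponents multiplied by 365.25: 1.35 (1.11 to 1.64).

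Data, model and p-value are the same; only the unit differs.

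**Step 3. Spread needed for all three numbers to print as 1.00.** For a positive effect the upper limit decides: (z + 1.96)·SE/SD must stay below ln 1.005 = 0.0049875. The smallest SD, in days, is:

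| N, p | SE per SD | z = 1.96 | z = 3 | z = 4 |
|---|---|---|---|---|
| 100, 0.5 | 0.200 | 157 | 199 | 239 |
| 100, 0.7 | 0.218 | 172 | 217 | 261 |
| 100, 0.9 | 0.333 | 262 | 331 | 398 |
| 60, 0.9 | 0.430 | 338 | 428 | 514 |

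On this approximation, an SD of about a year or more is enough in most rows.

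**Step 4. Stress test by simulation.** The approximation ignores skewness, so it was tested with N = 100, log-normal duration with median 300 to 700 days, and odds ratios of 1.6 to 2.5 per SD of log-duration, keeping only results with p<0.05.

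- Outcome proportion near 0.5: the odds ratio printed as 1.00 in 92 to 100%. All three numbers did so in at least 54% at a median of 300 days and at least 94% at 500 to 700 days.
- Outcome proportion 0.9, positive effect: all three printed as 1.00 in only 0 to 65%, rising with the median. In the least favourable settings the odds ratio itself did so in well under half.
- Outcome proportion 0.9, protective effect (odds ratio 0.5 per SD): mostly printed as 1.00 again.

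The weak case arises because the few patients without the outcome cluster at short durations, which makes the slope per day steeper than step 3 allows. These percentages move with the assumed distribution and form of effect, so they show where the problem is strong or weak and are not predictions.

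**The case against.** **The one-day increment is inferred.** No section says that duration enters the model per day, and only the titles of the table shells are visible. SAP 8.1.4 selects factors by chi-square or Fisher test alone, which an ungrouped day count cannot enter. This stands in part. But 8.2.2.2, 8.2.3.3 and 8.2.3.6 add univariate logistic regression, section 9 has continuous-factor tables, and days are the only unit given. Per day is the natural reading of the plan, though not an explicit one. A programmer may well rescale, but nothing in the SAP says so.

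**The outcome may be very common.** Table 27 analyses any adverse event regardless of causality, so a high proportion cannot be excluded, and step 4 shows that the full collapse then often fails for a positive effect. This stands. A reader might infer that a significant duration effect must print as 1.00 (1.00 to 1.00); the documents give neither the spread nor the outcome proportion needed to say so.

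**The effect might be recoverable elsewhere.** A reader might infer that direction and size are lost from the whole report. That is not shown: Tables 26, 34 and 38 may give means or medians by outcome group. What is at risk is the adjusted effect in Tables 27, 35 and 39.

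**Other continuous factors.** A reader might extend the point to body surface area, because an odds ratio per 1 m² covers a wide step, or to age and weight. The documents give no ranges that would show a defect there, and a reader who knows the unit can rescale such an odds ratio.

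**Conclusion.** The point holds as a minor reporting defect. If the plan is followed as written, on the per-day scale, any odds ratio for disease duration equivalent to about 0.16 to 6.18 per year prints as 1.00. That bound rests only on the rounding rule and the per-day reading.

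Whether both limits also print as 1.00 depends on quantities the documents do not give. It is usual when the SD of duration is about a year or more and the outcome proportion is moderate. It is not assured when the spread is small, or when the outcome is very common and the effect positive.

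The consequence is limited. It arises only if duration is selected at p<0.05, in an analysis that SAP section 4 treats as exploratory. No test, p-value or headline rate is affected.

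**What to change.** In SAP 8.2.2.2, 8.2.3.3 and 8.2.3.6, state that the odds ratio for duration of disease is per year (days/365.25), and that the unit of every other continuous factor is printed beside its odds ratio. Carry the units into Tables 26, 27, 34, 35, 38 and 39 wherever odds ratios appear. The descriptive summary of duration can stay in days.

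Two decimals then suffice, and 8.1.3 need not change. Moving to three significant figures without rescaling would not help: 1.0019 still prints as 1.00.

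The cost is a sentence of SAP wording and a label in the table shells. Data, tests and p-values do not change.

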8.1.4 Factorial Analyses

In order to explore the factors associated with the patient's safety and effectiveness profiles, the incidence proportion of AEs and last effectiveness rate will be analyzed by demographics and baseline characteristics factors. The Chi-square test or Fisher's exact test (depending on data counts as appropriate) will be used first to assess the impact for each background factor, and p-value will be outputted. The potentially important factors identified by Chi-square or Fisher's exact test p-values at 0.05 level will be further pooled and tested in a multivariate logistic regression model.

8.2 STATISTICAL ANALYSES

8.2.1 Demographics and baseline characteristics

8.2.1.1 Demographics and underlying disease information

- Age(years)
- Elderly(≥ 65 years)
- Gender: Male | Female
- Height(cm)
- Weight(kg)
- Body Surface Area(m^2 , Mosteller formula)

$$= \sqrt{\frac{W \times H}{3600}} = 0.016667 \times W^{0.5} \times H^{0.5}$$
- Pregnancy: Yes | No | NA
- Breast-feeding: Yes | No | NA
- Diagnosis:

- Philadelphia (+) B-cell ALL | Philadelphia (-) B-cell ALL | Unknown
- Duration of disease(day):
BESPONSA® administration start date – First diagnosis date + 1
- Current disease status:
Refractory | First relapsed | Second relapsed | Third or more relapsed
- Hepatic disorder: Yes | No
- Renal disorder: Yes | No

8.2.1.2 Prior treatment history of B-cell precursor lymphoblastic leukemia

All treatment drugs used in previous systemic therapy shall be divided by the order of regimen and summarized using frequency and percentage by ATC code level 1 and level 4.

- Previous systemic therapy: Yes | No | Unknown
- Number of previous systemic therapies:
One | Two | Three | Four | More than five
- Previous hematopoietic cell transplant: Yes | No | Unknown

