7.3.3.1. Previous systemic therapy

- Regimen: Record the name of regimen.
- Purpose of treatment: Select one among 'induction', 'consolidation', 'maintenance', 'conditioning', or 'intensification'.
- Name of treatment drug: Record generic name.
- Duration of administration: Record the start date and stop date. Record approximate date if an actual date is unknown.
- Best response to therapy: First, check among 'conducted', 'not conducted' or 'unknown'. If 'conducted', record the date of evaluation and select one among 'complete response (CR)', 'CR with incomplete blood count recovery (CRi)', 'refractory disease', or 'progressive disease'. Response Criteria is defined according to *'NCCN Guideline Version 2.2016 Acute Lymphoblastic Leukemia'*⁹. Refer to Appendix 1 for detailed Response Criteria.

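### SAP 8.2.1.2 has no category for a patient with exactly five previous systemic therapies

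*SAP*

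**What the plan says.** SAP 8.2.1.2 reports whether the patient had previous systemic therapy (yes, no or unknown) and then how many, in the categories "One | Two | Three | Four | More than five". It gives no rule for what counts as one therapy. The nearest indication is in the same section: "All treatment drugs used in previous systemic therapy shall be divided by the order of regimen".

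The source data are described in Protocol 7.3.3.1. Each record carries a regimen name ("Regimen: Record the name of regimen") and one purpose ("Purpose of treatment: Select one among 'induction', 'consolidation', 'maintenance', 'conditioning', or 'intensification"). Drug names, start and stop dates, and best response are also recorded. No line number is collected.

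The variable is used beyond the baseline description. SAP 8.2.2.2 summarises and tests "AEs according to the background factors in section 8.2.1 and special population set in section 5.3". SAP 8.2.3.3 does the same for "last effectiveness according to the background factors in section 8.2.1 and special population set in section 5.3", and SAP 8.2.3.6 repeats it for best overall response. In the final report, "potentially significant factors(p-value<0.05) identified in the univariate analyses will be further explored in a multiple logistic regression model"; the two effectiveness sections have an equivalent step.

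**The concern.** A set of categories should give every possible value exactly one place, and this one does not. A programmer who meets a count of five must leave the patient out, move the patient up to the top category, or move the patient down to four. The SAP does not choose among these. Section 7 excludes missing values, but a recorded five is not missing, so that rule does not settle it.

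The choice can change the row counts and denominators of the baseline summary. It can also change the chi-square or Fisher tests that decide whether the factor enters a multiple logistic model. If it is made during programming of the final report, it is made with the data in view.

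A second, lesser matter is that the counting unit is not stated. A count of records, of regimens or of lines of treatment could put the same patient in different categories.

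**Working it through.** The plan states no figure that depends on this point, so there is nothing to reproduce. The check is a mapping of counts to categories.

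**1. Mapping as printed (SAP 8.2.1.2).**

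| Count | Category |
|---|---|
| 0 | none in this item; covered by the answer No to previous systemic therapy |
| 1, 2, 3, 4 | One, Two, Three, Four |
| 5 | **none** |
| 6 or more | the top category |

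The top category requires a count above five, so its smallest member is six. Five is the only positive count without a place. This holds for any counting unit.

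**2. Mapping with a last category of five or more.** Counts 1 to 4 are unchanged and counts from 5 upward share the last category. Every count from one upward then has exactly one category.

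**3. How many patients.** The documents give no distribution of prior-therapy counts. Let q be the assumed share with exactly five, and take the 100 planned subjects (SAP 2.1). Expected number without a category = 100 × q. Chance of at least one = 1 − (1 − q)^100.

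| Assumed q | Expected number | Chance of at least one |
|---|---|---|
| 2% | 2 | 1 − 0.98^100 = 0.87 |
| 5% | 5 | 1 − 0.95^100 = 0.99 |
| 10% | 10 | above 0.99 |
| 20% | 20 | above 0.99 |

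These rows only restate the assumption. They show that even a small share would probably produce at least one such patient; they do not estimate the share.

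**4. Why the unit needs a sentence.** Suppose, for illustration only, that records were counted and that each line of treatment used between one and five of the five listed purposes, each at most once. Then L lines give from L to 5 × L records:

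- one line: 1 to 5
- two lines: 2 to 10
- three lines: 3 to 15
- four lines: 4 to 20
- five lines: 5 to 25

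A count of five could then come from any number of lines from one to five. If regimens or lines were counted, five would mean five regimens or five lines. The SAP does not say which applies.

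**The case against.** The strongest reply is that the last category is probably a slip for five or more, and that a programmer would read it so. That is plausible, and if so nobody is lost once the words are corrected. But the printed rule fails as it stands, and correcting it costs one phrase.

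A second reply is that little depends on the variable. SAP section 4 states no formal hypothesis and no definite conclusions from p-values, and SAP 6.4 says only that the baseline characteristics could be considered as covariates. Current disease status in SAP 8.2.1.1, which separates refractory disease from first, second and third or later relapse, partly captures previous treatment failures. All of this stands and limits the importance of the point. It does not supply a category for five.

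A reader might infer more than the documents support:

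- **That the SAP counts treatment phases, so the factor does not measure prior lines.** The SAP gives no counting rule, and the only unit it mentions is the regimen. It never calls the variable lines. The one-purpose-per-record layout makes a phase count possible but does not show that one is intended.
- **That the gap removes the most heavily pretreated patients.** Patients with six or more keep a category. Under a phase count, five records could even come from a single line.
- **That prior lines cannot be recovered because there is no salvage option.** Protocol 7.3.3.1 records regimen, dates and response, Protocol 7.3.2 records the date of each relapse, and Protocol 7.3.3.2 records transplant separately.

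**Conclusion.** The point holds as a category error: exactly five previous systemic therapies has no place in SAP 8.2.1.2, and the gap carries into the three factor analyses that draw on section 8.2.1. This follows from the printed text alone and needs no assumption about the counting unit.

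The number of patients affected is unknown. It may be none. The effect is confined to one baseline item and to exploratory models, so this is a minor correction. The missing definition of one therapy is a matter for clarification; it is not evidence that the variable is wrong.

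**What to change.** In SAP 8.2.1.2, change the last category to five or more, and carry the change into the baseline table and the factor-analysis tables. This is one phrase and needs no new data.

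As a secondary clarification, add a sentence saying what counts as one therapy: a record, a regimen or a line. If prior lines are intended, count the initial treatment programme as line one and add a line for each new regimen given for refractory or relapsed disease. Use the regimen, dates, response and relapse dates already collected. The initial programme must be counted explicitly. Otherwise a patient in first relapse after one programme would have zero lines and again no category.

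The definition costs a sentence in the SAP. If lines are chosen, it also costs a medical review of about 100 treatment histories. Both changes should be settled before the final re-examination analysis.
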